## **AIM 1: To assess the subjective and clinical effects of nicotine reduction on ENDS users.**

Objective and hypothesis. This aim will help understand users' response to NR and how it will influence their product satisfaction, nicotine dependence, intention to quit or use in the future, lung functions, and clinical symptoms. We hypothesize that NR will be associated with less satisfaction, withdrawal suppression, and intention to use in the future and that such an effect will be more pronounced in total compared to partial NR and in high compared to low-frequency users.

Outcomes. We will utilize our clinical lab model to study the effect of NR on the following outcomes assessed according to the plan described in Table 2. All assessments will be based on instruments that are standard in clinical lab studies of addictive behaviors modified for the ENDS we plan to use (Vargas-Rivera et al., 2020). Participants will use a tablet to respond to these measures using RedCap.

**Outcomes.** We will utilize our clinical lab model to study the effect of NR on the following outcomes assessed according to the plan described in Table 2. All assessments will be based on instruments that are standard in clinical lab studies of addictive behaviors modified for the ENDS we plan to use (Vargas-Rivera et al., 2020). Participants will use a tablet to respond to these measures using RedCap. Briefly, we will assess;

1. Demographic and baseline characteristics; including age, race, sex, and reasons for ENDS use. Other characteristics will include the frequency of ENDS use, and the history of other tobacco/nicotine products use (Amato, Boyle & Levy, 2016; Zavala-Arciniega et al., 2019; Vargas-Rivera et al., 2020).
2. Dependence measures including; 1) *Use satisfaction* (Modified Cigarette Evaluation Questionnaire (mCEQ) (Arger et al., 2017); 2) *Dependence* (Questionnaire of Smoking Urges-brief and the Minnesota Nicotine Withdrawal Scale, Penn State Electronic Cigarette Dependence Index (Ben Taleb et al., 2018; Foulds et al., 2015; St Helen et al., 2017); 3) *Puff sensory effects* (Duke Sensory Scale, (Malson & Pickworth, 2002)).

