3. Use related measures including 1) *Harm perception* (Smith, Curbow & Stillman, 2007); 2) *Intention to quit or use in the future* (Wackowski et al., 2016); 3) *Reasons for ENDS use* (Kinouani, Pereira & Tzourio, 2017), and 4) Visual Analogue Scale (VAS) to measure ENDS use experience such as pleasantness, enjoyment, and pleasure from use (as in Vargas-Rivera et al., 2020).
4. Lung function tests (LFTs): LFTs (i.e., lung volume testing, airway resistance, specific airway conductance) will be measured before and immediately after ENDS use (Carlos et al., 2019). According to 2019 American Thoracic Society and European Respiratory Society recommendation (Graham, Jacobs & Amato, 2019) simple spirometry (e.g. FVC, % predicted value (pred), FEV1 % pred FEV1/FVC, % pred); forced expiratory flow (FEF) and Peak expiratory flow rate or PEFR) will be performed. Diffusing capacity for carbon monoxide (DLCO) will be determined using a rapidly resolving gas analyzer (RGA) (Neder et al., 2019) and the single-breath technique (Graham et al., 2017).
5. Clinical symptoms, such as (dry mouth, eye irritation, palpitations, and nausea) will be assessed pre-post ENDS use using standard clinical assessments (McConnell et al, 2017; Morice et al., 2007). Symptoms like cough, sore throat will be assessed after-session since our participants will be free of these symptoms pre-session to exclude potential COVID-19 cases (pls. see Inclusion and Exclusion criteria).
6. Cardiovascular measures: To monitor participants' vital signs, physiological measures will be monitored during each session such as heart rate, blood pressure, and pulse oximetry using the Noninvasive Patient Monitor 507E, Criticare Systems, Waukesha, WI.

7. Three-month follow-up call: Assesses Harm perception (Smith, Curbow & Stillman, 2007), *nicotine preference*, and *changes in ENDS and tobacco use* (Amato, Boyle & Levy, 2016; Zavala-Arciniega et al., 2019; Vargas-Rivera et al., 2020).

Table 2: Measures * Only during baseline	Measurement time			
	Pre	During	Post	3 month
Demographics*	X			
Tobacco use history	X			X
ENDS Use satisfaction (mCEQ subscale)			X	
Penn State Electronic Cigarette Dependence Index (10 items)	X			
Questionnaire of Smoking Urges (7-point Likert scale)	X		X	
Minnesota Nicotine Withdrawal Scale (score range from 0-100)	X		X	
ENDS Visual analog scale (0 not at all to 100 extremely)			X	
Duke Sensory Scale (7-point Likert scale)			X	
Peer and family influence	X			
Harm perception	X		X	X

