## **AIM 2: To assess the puffing behavior in response to nicotine reduction.**

**Objective and hypothesis.** This aim will help understand users' compensatory puffing behavior in response to NR and its effect on plasma nicotine as the main substance sustaining addiction to ENDS. *We hypothesize that NR-related compensatory puffing will be more pronounced in high vs. low-frequency users.*

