Demographic data will be examined and compared to determine if there are significant between-group differences on measures that may be related to study outcome (some differences are expected due to design such as past 30-day ENDS use) though these are expected to be minimized due to randomization. Unexpected between-group differences will be considered as potential adjustment covariates in the primary analysis (Evans et al., 2006). We will generate descriptive statistics which include means, standard deviations, frequencies, and proportions depending on the scale of the outcome by NR factor, time and group assignment. Univariate comparisons of the outcomes by the mentioned conditions will consist of repeated measures ANOVA and paired t-test (for 2X2 within factors) and two-sample t-test for between factor, or their non-parametric equivalents (Wilcoxon signed-rank test and Friedman test for within factors and Wilcoxon Mann-Whitney U test for between factor) if the parametric assumptions are not met. ANOVA will be followed by multiple comparisons with Bonferroni adjustments for multiplicity. Analysis of categorical outcomes will involve a chi-square test of independence for between factors or McNemar's test for paired proportions. The primary analysis of each outcome will involve analysis of variance with two within-subject factors (nicotine concentration: (5%, 3%) or (0% 5%)) and time (pre-post-use). This approach will be extended into a mixed-effects linear regression model to adjust or study the effects of personal attributes such as sex, education, race, and SES. Furthermore, we will consider clinical/physiologic factors such as lung function and respiratory symptoms in a similar modeling approach described above, as a function of experimental factors and demographic covariates, in order to quantify the harm or disease risk. In a case of a non-linear relationship between these factors, we will apply outcome transformations or use non-linear splines to accurately describe these outcomes as a function of

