mentioned covariates. Given the known sex-related differences in nicotine dependence (Benowitz et al., 2006), to assess if sex has any effect on the results, it will be considered as a covariate and we will test the pre-planned interaction with it to determine the heterogeneity of the study outcomes by sex as well as potential differential effects. Similarly, for categorical outcomes we will apply generalized linear models and estimating equations with the same main effects as described above, modeling within factors as random effects. We will test for the carry-over effect statistically and will control for it when testing for the primary factors (Senn, 2002).

For Aim 3, we will use a one-way ANOVA to test the effect of NR on aldehyde emissions and multiple linear regression analysis to assess the influence of puff topography data (puff volume, duration, number, and interpuff interval) on aldehyde emissions. Additionally, we will measure the relation between the plasma nicotine levels obtained in the clinical lab and measured nicotine yields obtained in the analytical lab using linear regression. Significance levels will be adjusted for violations of the sphericity assumption using Huynh-Feldt corrections (Keppel, 1991). All differences will be considered significant at the alpha level of 0.05 using adjusted p-values where appropriate. Due to the nature of laboratory data collection, missing data is rare and it usually occurs due to instrument malfunction. All data are collected and checked for completeness by laboratory staff. In the case of missing data, which we expect to be minimal, we will use a regression model based on multiple imputations with all available outcome data, demographic, and clinical variables as predictors. This will be carried out in 25 random repetitions under missing at random assumption, analyzed using methods described above and results will be combined to produce unbiased overall estimates and standard errors of the experimental conditions. As a sensitivity analysis completers results will be compared with multiple imputation results.

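### For outcomes measured once per session, the commitment to test and control for carry-over names no term or rule, and taken literally it reduces the crossover to a session-1 comparison

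*Combined protocol and SAP*

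**What the plan says.** - On carry-over, the Statistical analysis section has one sentence, followed by a methods citation: "We will test for the carry-over effect statistically and will control for it when testing for the primary factors". No test statistic, model term, estimator or decision rule is given. The general level would apply to the test: "All differences will be considered significant at the alpha level of 0.05".
- On the main model: "The primary analysis of each outcome will involve analysis of variance with two within-subject factors". The factors are nicotine concentration and time (pre, post). Period, sequence and carry-over are not named.
- Design (Experimental protocol): two sessions per participant in counterbalanced order, 48 hours apart. Participants and recruitment adds 12-hour abstinence before each session, checked by plasma nicotine below 5 ng/ml.
- Table 2 schedules satisfaction, the visual analogue scale and the Duke Sensory Scale after use only, and puff topography during use only. The Statistical analysis section averages topography to one value per participant and condition.
- Hypotheses: for Aim 1, "We hypothesize that NR will be associated with less satisfaction, withdrawal suppression, and intention to use in the future"; for Aim 2, "NR-related compensatory puffing will be more pronounced in high vs. low-frequency users".

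**The concern.** With two sessions and two orders, an outcome with one value per session gives four cell means. Overall level, period, nicotine condition and carry-over use all four. Carry-over then occupies the same degree of freedom as sequence and cannot be adjusted for within participants. The commitment nevertheless applies to the tests of the primary factors.

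The satisfaction part of the Aim 1 hypothesis rests on such an outcome. At stake are the within-participant precision that a crossover offers, the validity of the p-value if a test decides the estimator, and a possible claim that carry-over was controlled when the estimate had not moved. With no rule written, the choice between estimates of very different precision stays open until the data are in hand.

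**Working it through.** **Inputs.** From Sample size: 120 evaluable (written as 2X60), 20% loss, f = 0.1 to 0.2, correlation rho = 0.5, alpha 0.05. For a two-level factor the difference is 2f, so 0.2 to 0.4 SD. Assumed: 60 per part with 30 per sequence, two-sided tests, outcome SD of 1, rho of 0.3 and 0.7 as a range, and all carry-over sizes.

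**The plan's own figures.** 120/(1 - 0.2) = 150, as stated. With N = 120 and four measures per person, the noncentral F distribution gives 86.7% power for a within factor at f = 0.1 and 78.5% for a between factor at f = 0.2. The claim of at least 80% is therefore essentially reproduced for the pooled 120. The plan gives no figure for carry-over.

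**What each contrast estimates.** Let tau be the nicotine effect, and lambda the differential carry-over into session 2 of sequence A, which takes the higher concentration first. A1 to B2 are the cell means.
- Within-participant: ½[(A1 - A2) - (B1 - B2)] = tau - lambda/2.
- Session 1 only: A1 - B1 = tau.
- Sequence contrast: (A1 + A2) - (B1 + B2) = lambda.

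**Reading 1: always adjust.** With lambda in the model, the nicotine estimate is A1 - B1.
- Within SE = sqrt((1 - rho)/30) = sqrt(0.5/30) = 0.129.
- Session-1 SE = sqrt(2/30) = 0.258.
- Variance ratio = 2/(1 - rho) = 4.0 (2.9 at rho 0.3; 6.7 at rho 0.7). It does not depend on N.

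| Nicotine main effect, rho 0.5 | Within | Session 1 |
|---|---|---|
| 60 per part, f = 0.2 | 86% | 33% |
| 60 per part, f = 0.1 | 33% | 12% |
| 120 per part, f = 0.2 | 99% | 58% |
| 120 per part, f = 0.1 | 58% | 19% |

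**Reading 2: test at 0.05, then switch to session 1 if significant.** Under no nicotine effect and no carry-over, simulation with 30 per sequence gives a type I error of about 7.3% at rho 0.5 (about 7.0% at 0.3 and 7.9% at 0.7; repeat runs differ by about 0.1 point). The cause is that the session-1 test shares data with the carry-over test. The carry-over contrast has SE = sqrt(8(1 + rho)/60) = sqrt(12/60) = 0.447, so it detects a carry-over of 0.2 SD 7% of the time and one of 0.4 SD 14% of the time.

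**Reading 3: add a sequence term.** In a simulated dataset with carry-over, the nicotine estimate was 0.1477 (SE 0.1375) both with and without the term. An explicit carry-over term instead returned the session-1 estimate, 0.015.

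**Aim 2 is a different contrast.** Its hypothesis is a nicotine-by-use-frequency interaction, so carry-over equal in both frequency groups cancels. Assume two groups of 30 (15 per sequence), rho 0.5 and an interaction of 0.4 SD. The within SE is sqrt(2 x 0.5/15) = 0.258 and the session-1 SE is sqrt(2 x 2/15) = 0.516. Power is about 33% and 12%.

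**Pre-post outcomes.** Carry-over that is equal before and after use in session 2 cancels from the nicotine-by-time contrast. Change-score power at 0.4 SD stays at 58% (SE 0.183). Bias remains only if carry-over alters the response to use.

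**When session 1 would be better.** The within estimate has bias lambda/2. At lambda = 0.2 its root-mean-square error is sqrt(0.129² + 0.1²) = 0.163, against 0.258 for session 1. They are equal at lambda = 2 x sqrt(0.258² - 0.129²) = 0.447 SD (0.316 SD with 120 per part).

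**The case against.** The strongest reply is that this is missing detail, not a faulty analysis. The sentence carries a methods citation whose procedure cannot be seen here, and the design protects against carry-over through the washout, counterbalancing and the abstinence check. It stands that no particular procedure is stated. A reader might infer that the plan will test first and then switch estimators, but it does not say so. The 7.3% therefore belongs to a possible reading only, and it is a moderate inflation. A reader might also infer that carry-over is present; nothing in the documents shows that.

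The three readings are not exhaustive. Pre-use plasma nicotine, urges and withdrawal could serve as session-level covariates for satisfaction or puffing. That would address residual nicotine or withdrawal without falling back on session 1, although not learning or expectancy. The plan does not propose it.

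The gap could also be closed by writing down a rule instead of removing the commitment. But a rule built on a carry-over term or on the test brings the costs shown above. The design safeguards support stating the assumption openly more than they support a weak test that can change the primary estimate.

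**Conclusion.** The point holds for the nicotine main effect on outcomes with one value per session. The commitment is undefined, and carried out literally it multiplies the variance by 4 at the plan's own correlation (2.9 to 6.7 over the assumed range). The power losses rest on the assumed 60 per part. At f = 0.1 within-participant power is already only 33%, so removing the adjustment does not by itself make that effect detectable.

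Three wider readings are not supported:
- The main-effect figures do not describe the Aim 2 hypothesis, which is an interaction with low power on either analysis.
- They do not describe outcomes with pre and post values, where the cost is smaller and depends on the form of carry-over.
- Aim 3 emissions have their own one-way ANOVA and are outside this point.

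This should be corrected before analysis.

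**What to change.** In the Statistical analysis section:
- Remove the commitment to let a carry-over test or term alter the primary analysis.
- For each part, pre-specify one within-subject model with nicotine condition, session (period) and, for pre-post outcomes, time. A sequence term is optional and should not be described as controlling carry-over.
- State the no-carry-over assumption and base it on the existing 48-hour washout, 12-hour abstinence and plasma nicotine check.
- Report the session-1-only estimate as a sensitivity result.
- Report session-2 pre-use values by sequence for every outcome that has them: urges, withdrawal, plasma nicotine, lung function, intention to quit or use, harm perception, and the symptoms assessed before and after use.

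The cost is SAP wording; no new data are needed. The downside is that the primary analysis openly relies on the washout. Single-value outcomes have no pre-use value of their own with which to check it, and session 1 would be the more accurate estimate if carry-over exceeded about 0.45 SD. That is the reason to keep it as a sensitivity result.

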## **Study Aims**

Aim 1. To assess the subjective and clinical effects of NR on ENDS users. Participants will undergo 2 ENDS use sessions that are preceded by 12-hour abstinence, with session order counter-balanced to mitigate order and carry-over effects. This study will focus on pre-post-use assessment of craving, withdrawal, satisfaction, intention to quit or use in the future, lung functions (e.g. FEV1 % predicted; FEV1/FVC, CO diffusing capacity-DLCO), and symptoms (e.g. dry mouth, eye irritation, palpitation, nausea). This aim will show ENDS users' response to NR on product satisfaction, dependence, lung functions and symptoms.

Aim 2. To assess puffing behavior in response to NR. Under the same protocol, puff topography (e.g. puff volume, puff frequency, duration) will be assessed continuously during the 2 sessions, while plasma nicotine will be measured pre-post sessions to assess nicotine boost and its correlation to puffing parameters. This aim will help understand users' compensatory puffing in response to NR and its effect on plasma nicotine.

Aim 3. To assess exposure to toxicants associated with NR. We will measure toxicant emissions (14 aldehydes) in the analytical lab using a smoking robot that reproduces the puff-by-puff behavior (playback) of each participant for all two nicotine conditions (Aims 1, 2). This aim will reveal how compensatory puffing behavior in response to NR influences acute exposure to pulmonary toxicants.

The proposed studies will give clear evidence on the potential of NR regulations to limit the addictiveness and use of ENDS, and to help predict any potential side effects of NR on ENDS users.

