## **Study Design**

This study is divided into 2 parts (studies), whereby the first part will be 2X2 comparing NJOY 5% and 3% to test the effects of partial nicotine reduction, and the second part will be using the NIDA Standardized Research Electronic Cigarette (SREC) for Clinical Research 5% and 0% (placebo), to test the effect of the total reduction using the same pods and juices from the same manufacturer.

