Screening, and informed consent: Individuals who are identified as potentially eligible based on the phone screening will be asked to attend an onsite-screening, which will involve assessment of inclusion/exclusion criteria, physical examination, COVID-19 screening, and urine pregnancy testing for women. Prior to screening, potential participants will undergo a review of the study and consent procedures to ensure that they understand the study, its risks/benefits, and their rights as research participants. Consented (written) individuals will then undergo a physical examination conducted by the research nurse, who will have access to an on-call Medical Monitor (physician) in case of concern or for consultation at any point of the study as it is the standard practice in our lab. Successfully consented participants will be scheduled for their 1st session and asked to abstain from all tobacco/nicotine use 12 hours prior to it.

Sample size. All power calculations were performed with PASS19 (PASS, 2019). We built our calculation of the sample size for this study based on our preliminary study of the effect of NR on subjective (e.g. craving, urges) and puff topography measures (pls. see Preliminary Studies), where medium effect size (Cohen's  $f=0.2$ ) depending on nicotine condition was detected. Expecting a maximum 20% loss due to noncompliance with abstinence or study protocol (Vargas-Rivera et al., 2020), this study will include a dropout inflated sample of 150 ENDS users. Using repeated measures ANOVA F-test with 2 within and 1 between factors, a total dropout adjusted sample size of 120 (2X60) participants will have at least 80% power to detect small to medium-size effect (Cohen's  $f=0.1-0.2$ ) or larger for 2 within-subject (NR condition and time) and 1 between subject (use frequency) factors, as well as their interactions at 0.05 level of significance, assuming sphericity and a moderate correlation (0.5) among repeated measures (Cohen, 1988).

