Intention to quit or use in the future	X		X	X
Nicotine preference, changes in ENDS use				X
Reasons for ENDS use	X			
Puff topography (puff volume/ml, duration/sec; inter-puff interval/sec)		X		
Cardiovascular measures (BP; HR; oximetry)		X		
Plasma nicotine (ng/ml)	X		X	
Nicotine (playback)			X	
Aldehydes (playback)			X	

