## **AIM 3: To assess exposure to toxicants associated with nicotine reduction.**

**Objective and hypothesis:** This aim will help elucidate how compensatory puffing behavior in response to NR affects exposure to pulmonary toxicants. *We hypothesize that partial but not total NR will be associated with compensatory puffing behavior that will, in turn, lead to greater exposure to toxicants.*

**Analytical methods.** The analytical assessments will be conducted at the AUB Aerosol Research Laboratory (ARL). The ARL is equipped with two digital playback smoking machines necessary for Aim 3. These two machines, developed and tested by our team at AUB, are to our knowledge unique to this setting and are not available in any other laboratory. The proposed work in Aim 3 is built on the ARL framework and infrastructure for aerosol generation, sampling, and chemical analysis.

**Aerosol generation and sampling:** The deidentified puff topography data will be shared via Microsoft Sharepoint between FIU and AUB Aerosol Lab, thus, all communication will be encrypted between client and server using SSL 2048 bit keys. Access to the lab and data will be granted only by permission of Drs. [name] (PI), and [name] (local PI at AUB).

Once the puff topography files have been received by the ARL, we will use ALVIN (Aerosol Lab Vaping Instrument) (Talih et al., 2015, 2017) to draw aerosols from the ENDS devices, for each of the 240 topography sessions. For each session, ALVIN will be programmed to reproduce the puff topography data generated in the clinical lab. The generated aerosol will be drawn through a Gelman type A/E 47mm glass fiber filter followed by a 2,4-dinitrophenylhydrazine-coated silica cartridge (type LpDNPH H10) cartridge, for nicotine and aldehydes quantification, respectively (see Talih et al., 2015, 2017; El-Hellani et al., 2018 for more detail). The pods (e.g. JUUL) and batteries will be shipped from the same batch as those used at FIU to minimize biases. A new pod will be used for every session. Each pod will be pre-conditioned before sampling by drawing 15 4-second puffs at 1 LPM using ALVIN. We will use a quality assurance protocol and ENDS electrical performance tester developed at the ARL to ensure that each battery and pod are within tolerance (Talih et al., 2019, 2020b).

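### Aim 3 names a one-way ANOVA and two linear regressions with no participant term, although each participant supplies two playback records

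*Combined protocol and SAP*

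**What the plan says.** The study has two parts, each a two-session crossover. The first part is described as "comparing NJOY 5% and 3% to test the effects of partial nicotine reduction"; the second compares SREC 5% with 0% (Study Design).

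For Aim 3, a smoking machine "reproduces the puff-by-puff behavior (playback) of each participant for all two nicotine conditions" (Study Aims). Aerosol is collected "for each of the 240 topography sessions" (Aim 3, aerosol generation and sampling), so every participant has two records, one per concentration. The hypothesis is that "partial but not total NR will be associated with compensatory puffing behavior that will, in turn, lead to greater exposure to toxicants".

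The Statistical analysis section gives Aim 3 its own methods: "we will use a one-way ANOVA to test the effect of NR on aldehyde emissions and multiple linear regression analysis" on the topography variables, then a linear regression linking plasma nicotine to machine nicotine yield. No paired, repeated-measures, mixed-model or participant term is attached to any of the three.

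The general text of the same section is different: "The primary analysis of each outcome will involve analysis of variance with two within-subject factors", namely nicotine concentration and pre-post time. It also lists repeated-measures ANOVA and paired t-tests for univariate comparisons. A Huynh-Feldt sphericity correction is mentioned directly after the Aim 3 methods. The sample size paragraph calculates power "assuming sphericity and a moderate correlation (0.5) among repeated measures".

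**The concern.** A one-way ANOVA in its ordinary sense treats the two records of one person as coming from different people. If yields correlate within person, stable differences in puffing style between people stay in the error term. The test is then conservative, and a real rise in toxicant yield is easier to miss.

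This matters because the Aim 3 hypothesis predicts an increase for partial reduction and none for total reduction. In the SREC part a non-significant result is therefore the predicted result, and a test that discards the pairing makes it easier to obtain by default.

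The regressions have a related fault. With two records per person and no allowance for it, their standard errors are unreliable. The direction is not fixed: it depends on how strongly predictor and residual each correlate within person, and on how far puffing shifts between conditions.

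**Working it through.** **Plan's own figures.** 120/(1 − 0.20) = 150, the inflated sample. 120 × 2 = 240, the playback records. Within-subject power by the noncentral F uses λ = f²·N·m/(1 − ρ) with 1 and N − 2 degrees of freedom. With N = 120, ρ = 0.5 and m = 4 measurements (two conditions, pre and post), power is 86.7% at f = 0.1, consistent with the stated 80% or more for within-subject factors. That calculation relies on pairing.

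**What applies to aldehydes.** Table 2 marks playback aldehydes at one time per session, so m = 2. Each part has its own contrast, and I take 60 participants per part (120 over two parts; the plan writes 2X60 without saying what the split is by). At f = 0.2, λ = 0.04 × 60 × 2/0.5 = 9.6 and power is 86%. The smallest f with 80% power is 0.184.

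**Paired against one-way.** Take unit SD, n = 60 pairs, within-person correlation ρ and mean shift d = 2f.

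- True variance of the mean difference: 2(1 − ρ)/n.
- Variance used by an independent-groups one-way ANOVA: about 2/n.
- Ratio: 1/(1 − ρ), so the interval is 1/√(1 − ρ) times as wide.

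Worked case, ρ = 0.5 and d = 0.4:

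- The true SE is √(2 × 0.5/60) = 0.129, so d/SE = 3.10.
- The one-way test needs an estimate above 1.98 × √(2/60) = 0.361, which is 2.80 true SEs. Power is about Φ(3.10 − 2.80) = 0.62, and type I error about 2(1 − Φ(2.80)) = 0.5% (0.6% by simulation).
- The paired test needs 2.00 SEs. Power is about Φ(3.10 − 2.00) = 0.86.

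Simulation, 100,000 datasets per setting, two-sided 5%:

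| ρ | One-way type I error | Power d = 0.4 (f = 0.2): one-way / paired | Power d = 0.2 (f = 0.1): one-way / paired | Interval width ratio |
|---|---|---|---|---|
| 0.1 | 3.8% | 0.59 / 0.62 | 0.18 / 0.20 | 1.05 |
| 0.3 | 2.0% | 0.60 / 0.73 | 0.15 / 0.25 | 1.20 |
| 0.5 | 0.6% | 0.62 / 0.86 | 0.11 / 0.33 | 1.41 |
| 0.7 | 0.05% | 0.65 / 0.98 | 0.06 / 0.50 | 1.83 |

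Only ρ = 0.5 comes from the plan, as a general figure; the other values show the range.

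**Regressions.** 120 participants × 2 records, true slope 0, 40,000 datasets per setting. The intraclass correlations (ICC) and the shift in the predictor between conditions are all assumptions.

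| Predictor ICC | Residual ICC | Shift (SD) | Ordinary regression, type I error | Participant-clustered SE |
|---|---|---|---|---|
| 0.3 | 0.1 | 0 | 5.3% | 5.4% |
| 0.5 | 0.2 | 0 | 6.1% | 5.5% |
| 0.5 | 0.5 | 0 | 7.9% | 5.4% |
| 0.7 | 0.7 | 0 | 11.1% | 5.8% |
| 0.5 | 0.5 | 1 | 6.3% | 5.4% |
| 0.5 | 0.5 | 2 | 3.6% | 5.1% |

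**The case against.** The strongest reply is that a one-way repeated-measures ANOVA was meant. One-way counts factors and does not by itself imply independent groups. The general text names repeated-measures ANOVA and paired t-tests. A sphericity correction makes sense only for repeated measures, and it follows the Aim 3 methods in the same paragraph. The missing pre-post factor is not peculiar to aldehydes either: satisfaction, the visual analogue scale and the Duke scale are also post-only, so the general model is loosely worded throughout, and dropping time leaves a single within-subject factor.

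This makes a repeated-measures intent possible, but does not establish it. The paired-test sentence is qualified as being for the 2X2 within factors, and the Aim 3 text then names its own test without the repeated-measures label used elsewhere. With two conditions per participant, sphericity holds trivially, so the correction changes nothing. If that intent is confirmed, the ANOVA figures above fall away.

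Three further points stand in part:

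- In the aldehyde regression the person acts only through puffing, which supplies the regressors. With predictor ICC 0.7 and no residual correlation, type I error is 4.8%, so that regression may be little affected. Plasma on yield is the more plausible problem.
- A conservative test also makes the partial-reduction half of the hypothesis harder to support, so it does not favour the hypothesis as a whole.
- Pairing alone does not turn a non-significant result into evidence of no increase; that needs the confidence interval.

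**Conclusion.** The concern holds for the text as written. The Aim 3 methods specify no participant term for paired data, and the general text neither fits playback aldehydes as worded nor reaches the two regressions.

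At the plan's correlation of 0.5 with 60 pairs per part, an independent-groups ANOVA lowers power at f = 0.2 from 86% to 62%, below the plan's 80% target, and widens the interval by 41%. The size rests on a correlation the plan does not give for aldehydes; at 0.1 little is lost. The regression error ranges from slightly conservative (3.6%) to about double the nominal level (11.1%), entirely under assumed correlations.

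This should be fixed before analysis. The design and the data to be collected are unaffected.

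**What to change.** State the Aim 3 models explicitly.

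1. Within each part (NJOY 5% v 3%; SREC 5% v 0%), replace the one-way ANOVA with a linear mixed model having a participant random effect and fixed nicotine, period and sequence effects. A paired test is the minimum that cures the defect.
2. Report the within-person difference in aldehyde yield with its confidence interval. Judge the claim of no increase under total reduction on that interval, not on p > 0.05.
3. Fit both regressions with a participant random intercept or participant-clustered standard errors, and add a part/device term where the two parts are pooled.

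If repeated measures was always the intent, item 1 only records it and removes a choice that would otherwise be made after the data are seen. The cost is SAP wording, using standard software, with no new data and no change to randomisation or sample size.
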